#### *Waiver of consent justification*

A waiver of consent is requested as this study is no more than minimal risk to the study population.

When a patient requests an epidural, written consent is required in order for the provider to place the epidural. Thus, this study only involves patients who have consented to receive a standard of care epidural, as requested by the patient themselves. No patient will be asked to undergo an epidural placement procedure that they have not requested. Currently, this written consent to an epidural placement procedure at the University of Michigan von Voitlander Women's hospital implies a consent to have an epidural placed using either the Arrow® or B.Braun® pain management kit, depending on availability.

By changing to block randomization, this would not be a significant deviation from the provider's choice of pain management kits. The pain management kit available to place an epidural at a given time is subject to different influences that do not make it much different from

random. Most of the time, the provider uses whatever currently available is in the closet, whether the Arrow or BBraun kit.

There are logistical difficulties of obtaining informed consent from this vulnerable population (pregnant women in all stages of labor): (5)

- (1) Patients in labor (particularly the later stages of labor) are temporarily incapacitated and unable to give true informed consent.
- (2) Placing an epidural during labor (particularly the later stages of labor) occurs under time constraints where patient comfort is paramount to any research interests. We want to prevent any time delays in the anesthesiologist's administration of the requested epidural procedure.
- (3) Approaching laboring patients and requesting that they participate in a research study has the potential to incur significant distress in this patient population, especially as many are temporarily incapacitated due to labor pain.

We request a waiver of consent only as we feel that all patients will have received an epidural placement procedure that upholds the current standard of care at Von Voigtlander, and that this study does not endanger patient safety. Furthermore, should the provider feel that participating in this study is not in a patient's best interest, the provider can proceed using whatever pain management kit they feel is best.

We also want to avoid bias. Recruitment sampling of patients in only the early stages of labor (rather than all stages of labor) would increase the risk of bias in the study. By sampling from all patients who request an epidural, our sample would be an ideal sample since women who want to get any form of neuraxial analgesia or anesthesia often decide when they are

experiencing pain during labor. (6) As labor advances and the laboring parturient experiences more pain, it becomes more difficult to place an epidural as the patient may:

- find it difficult to sit in the ideal position for threading an epidural
- find it difficult to remain still for the time required to place the epidural

We want to sample from an accurate representation of all the scenarios that an anesthesiologist provider is called on to administer an epidural, all which necessarily involve threading an epidural catheter into the epidural space.

### *Study Size*

In order to determine the study size, we looked at 114 consecutive epidural placements as part of our routine quality assurance with the Arrow® Epidural Catheterization Kit at Von Voigtlander. We found that in 11% (n=12) of epidurals placed, the epidural catheter did not thread on the first attempt. In a separate quality assurance check we retrospectively reviewed 100 epidural placements finding out that in 1% (n=1) of epidurals placed, the epidural catheter did not thread on the first attempt. A sample-size analysis for the primary outcome shows that 107 epidural placements per group would provide a power of 80% to detect a difference in proportion between the two techniques of 0.10 at the 0.05 level. Considering an attrition of 10-20% for follow-up and data missing, a total number of 240 epidural placements will be collected. Power calculations were computed using PASS 14.

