### *Randomization Procedure*

Epidural kits are available for eligible patients on labor and delivery Von Voiglander 9th floor who are requesting labor analgesia. Approximately 30 epidural placements occur in the obstetric service during any given week. These epidural placements are consistently performed by residents, faculty, and fellows in a sharable and equitable number. No group of individuals are specifically targeted.

A prospective alternating intervention study design with randomized weekly scheduling will allow for equal use of the two epidural kits. In weeks randomized to Arrow®, only Arrow®

kits will be available. In weeks randomized to B.Braun®, only B.Braun® epidural kits will be available. In order to target a sample size of 240 epidural placements (n=120/group), and assuming that every week 30 epidurals will be performed, in 8 weeks we should be able to finish the study. However, if at the end of the 8 weeks we have not reached the target sample size per kit group, we will continue to randomize kit use in the following weeks in order to achieve sufficient sample size. The randomization of the kit to be exclusively used each week will be generated through a password-secure computer ([www.randomization.com](http://www.randomization.com)) by the research assistant. The two available kits are:

1) FlexTip Plus® Epidural Catheterization Kit (Arrow® International, Cleveland, OH).

**OR**

2) Multi-orifice epidural kit: Perifix® FX Springwound Epidural Catheter Kit (B.Braun Medical Inc., Bethlem, PA).

However, the alternate pain management kit will remain accessible during the study if it is deemed necessary for a particular patient.

This study design is in consideration of the fact that retrospective analyses of large databases or patient records are subject to unknown biases, thus causation is difficult to assign.

(3) (4)

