### *Statistical Analysis*

Statistical analysis will be performed using SAS 9.3 (SAS Institute, Cary, NC). The

primary outcome will be the success rate of epidural catheter threaded with each epidural kit, which will be compared by group using a chi-square test or Fisher's exact test, as appropriate. The secondary outcomes will be analyzed as follows: the difference in number of epidural attempts will be compared using the Mann-Whitney test; the difference in time to perform the epidural start to finish defined as the time the epidural needle is inserted through the patient's skin to the end of the catheter thread will be compared using the Student's t-test; the difference in the incidence of epidural needle manipulations once the epidural space has been established will be compared using the Chi-Square or Fisher's exact test, as appropriate; the difference in incidence of unintended dural puncture, paresthesia, and intravascular cannulations will be compared using the chi-square or Fisher's exact test, as appropriate. In addition, the difference in unsatisfactory labor analgesia with Arrow® and B.Braun® kits will be compared through the chi-square or Fisher's exact test, as appropriate, by looking at the difference in percentages of patients who have a verbal analogue pain score equal or less than 10 (scale 0 to 100) at 30 minutes following epidural medication administration. A p-value of 0.05 throughout will be considered statistically significant.

All statistical analyses will be performed using SAS 9.3 (SAS Institute, Cary, NC).

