#### *Monitoring and Quality Assurance*

The accuracy and completeness of all documents will be monitored on an on-going, weekly basis by the principal and co-investigator. All data will be collected at the time of each epidural placement, analyzed for completeness, and filed. The principal investigator and co-investigators will follow the validity and integrity of the data and adherence to the IRB approved protocol.

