**Table 2 Demographic and Epidural data collection**

Characteristics	Single-orifice N=125)	Multi-orifice N=125)	P-value
Demographics			
Age, years	XX ± X	XX ± X	X
Body Mass Index, kg/m 	XX ± X	XX ± X	X
Gestational age, weeks	XX ± X	XX ± X	X
Pain relief within 30 minutes	X (x%)	X (x%)	X
Cervical dilation (cm)	XX ± X	XX ± X	X
Catheter failure to advance	X (x%)	X (x%)	X
Dural puncture epidural	X (x%)	X (x%)	X
Accidental dural puncture	X (x%)	X (x%)	X
Paresthesia	X (x%)	X (x%)	X
Intravascular cannulation	X (x%)	X (x%)	X
Time to catheter thread	X (x%)	X (x%)	X
Number of epidural attempts	X (x%)	X (x%)	X
Epidurals replaced	X (x%)	X (x%)	X

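### The 240 placements are justified by 10–20% attrition, but 120 per group keeps the required 107 only up to 10.8% loss

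*Combined protocol and SAP*

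**What the plan says.** The Study Size section takes its rates from two quality assurance reviews. For the Arrow kit, "We found that in 11% (n=12) of epidurals placed, the epidural catheter did not thread on the first attempt", out of 114 placements. The second review found 1 in 100. From these it derives its requirement: "107 epidural placements per group would provide a power of 80% to detect a difference in proportion between the two techniques of 0.10". The significance level is 0.05. It then sets the total as follows: "Considering an attrition of 10-20% for follow-up and data missing, a total number of 240 epidural placements will be collected".

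The Randomization Procedure section repeats the total and splits it equally: "In order to target a sample size of 240 epidural placements (n=120/group"). If that target has not been reached after eight weeks, "we will continue to randomize kit use in the following weeks in order to achieve sufficient sample size".

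The Statistical Analysis section names the test for the primary success rate, "which will be compared by group using a chi-square test or Fisher's exact test, as appropriate". The shell of Table 2 carries a different group size, "Single-orifice N=125", with the same number for the multi-orifice column.

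**The concern.** An attrition range offered as the reason for a total is naturally read as covered by that total. Here the requirement (107), the allowance (10–20%) and the total (240) stand in consecutive sentences, and the three do not fit together: almost all of the range lies beyond what 240 can absorb.

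The practical risk is in how the sentence is used. The investigators check completeness weekly, and extra weeks are randomized only if the target is not met. Someone relying on the Study Size section could treat 15% or 20% missing forms as already budgeted, when a group of 120 falls below 107 at the 14th lost placement.

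**Working it through.** **Inputs.** Study Size: 11% (12/114) and 1% (1/100) first-attempt failure, a difference of 0.10, level 0.05, power 80%, 107 per group, attrition 10–20%, total 240. Randomization Procedure: 120 per group. The plan states neither the sidedness nor the formula. Both are inferred below because they reproduce 107.

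**1. Reproducing 107.** Two-sided comparison of two proportions, with p1 = 0.11, p2 = 0.01, mean 0.06, d = 0.10:

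- Uncorrected: n0 = [1.960·√(2·0.06·0.94) + 0.8416·√(0.11·0.89 + 0.01·0.99)]² / 0.10² = 87.3, so 88.
- Continuity-corrected: n = (n0/4)·[1 + √(1 + 4/(n0·d))]² = 106.4, so **107**, an exact match.

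**2. What 120 per group can lose.** 120 − 107 = 13, and 13/120 = 10.8%.

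**3. What the stated range needs.** Remaining = 120·(1 − loss). Needed per group = 107/(1 − loss), rounded up.

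| Loss | Remaining of 120 | Against 107 | Needed per group | Needed in total |
|---|---|---|---|---|
| 10% | 108 | +1 | 118.9 → 119 | 238 |
| 15% | 102 | −5 | 125.9 → 126 | 252 |
| 20% | 96 | −11 | 133.75 → 134 | 268 |

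**4. Could another inflation rule explain 240?** Multiplying instead of dividing gives 107 × 1.10 = 117.7, so 118 (236 in total), and 107 × 1.20 = 128.4, so 129 (258 in total). That shortcut also misses the upper end; 120/107 = 1.12, so 240 corresponds to about 12% on it.

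**5. Does the Table 2 size explain it?** With 125 per group the tolerated loss is 1 − 107/125 = 14.4%, and 20% loss leaves 100. It is still short.

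**6. Power with 96 per group** (two-sided 0.05, independent placements):

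| Method | 11% vs 1% | 12/114 (10.5%) vs 1% |
|---|---|---|
| Continuity-corrected formula (the basis of 107) | 74.8% | 71.7% |
| Fisher's exact test, exact enumeration | 81.8% | 78.5% |
| Uncorrected chi-square, exact enumeration | 88.9% | 86.6% |

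For 11% versus 1%, the usual normal approximation for the uncorrected chi-square gives 83.6%, below the enumerated 88.9%. With 107 per group the continuity-corrected figure is 80.3%, consistent with the plan's 80%.

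**The case against.** The strongest reply is that little is lost in practice. The analysis will use chi-square or Fisher, and at the planned rates both keep more than 80% power with 96 per group. That is correct for 11% versus 1%, and it is why this point concerns the allowance and not the adequacy of the trial. It is not fully secure: at the observed 12/114, Fisher falls to about 78%.

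A second reply is that the upper end of the range may not concern the primary outcome. Threading is recorded at the procedure ("All data will be collected at the time of each epidural placement, analyzed for completeness, and filed"), whereas the 30-minute pain score needs follow-up. Loss on the primary outcome may well be near or below 10%. But the plan does not divide the 10–20% by outcome and attaches it directly to the total built on the primary outcome's 107.

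Third, the plan never says outright that 107 are kept at 20%, and the lower end does work (238 needed, 240 planned). Both statements are true. Yet the whole range is given as the reason for 240, and everything above 10.8% is uncovered.

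Fourth, recruitment can be extended. The only target named for that extension is 120 per group, and nothing says that incomplete placements are replaced. Weekly completeness checks would make a shortfall visible but do not fill it.

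**Conclusion.** The concern holds. The total of 240 keeps 107 per group for losses up to 10.8% (13 placements in a group), not across 10–20%. At 15% loss a group is 5 short and at 20% it is 11 short; covering 20% would take 268 placements. This follows from the plan's own figures and does not depend on which inflation rule or which table is used.

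The consequence for power is modest and depends on method and rates: between about 72% and 89% with 96 per group over the methods and rates shown. Those values treat placements as independent although kits are allocated by week, so they should be read as indicative. The correction is worth making because the error sits in the sample-size justification and costs almost nothing to remove.

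**What to change.** Restate the attrition sentence in Study Size, for example:

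> A total of 240 placements (120 per group) preserves the required 107 per group for attrition up to 10.8% (13 placements per group); at 20% attrition, 96 per group would remain.

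If a power figure for 96 per group is added, give its method, the assumed rates and the independence assumption. This costs one sentence and changes nothing in design, analysis, planned size or duration.

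If the team expects losses near 20% on the primary outcome and wants 107 evaluable per group, the alternative is to raise the total to 268. That is 28 more placements. At the stated 30 per week, with one kit per week, 134/30 = 4.5, so five weeks per kit would be needed instead of four, or ten weeks instead of eight.

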### *Statistical Analysis*

Statistical analysis will be performed using SAS 9.3 (SAS Institute, Cary, NC). The

primary outcome will be the success rate of epidural catheter threaded with each epidural kit, which will be compared by group using a chi-square test or Fisher's exact test, as appropriate. The secondary outcomes will be analyzed as follows: the difference in number of epidural attempts will be compared using the Mann-Whitney test; the difference in time to perform the epidural start to finish defined as the time the epidural needle is inserted through the patient's skin to the end of the catheter thread will be compared using the Student's t-test; the difference in the incidence of epidural needle manipulations once the epidural space has been established will be compared using the Chi-Square or Fisher's exact test, as appropriate; the difference in incidence of unintended dural puncture, paresthesia, and intravascular cannulations will be compared using the chi-square or Fisher's exact test, as appropriate. In addition, the difference in unsatisfactory labor analgesia with Arrow® and B.Braun® kits will be compared through the chi-square or Fisher's exact test, as appropriate, by looking at the difference in percentages of patients who have a verbal analogue pain score equal or less than 10 (scale 0 to 100) at 30 minutes following epidural medication administration. A p-value of 0.05 throughout will be considered statistically significant.

All statistical analyses will be performed using SAS 9.3 (SAS Institute, Cary, NC).

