## BACKGROUND

Identification of the epidural space involves recognition of a change in pressure from one tissue plane to another. This drop of pressure, called “loss of resistance” (LOR), across a band of connective tissue into the epidural space is detected using a needle-syringe apparatus. The operator applies pressure to the plunger of the syringe until the drop in pressure is identified when the plunger collapses. The epidural catheter, a small tube that is inserted into the epidural space to give the medication, is then advanced using the needle as a guide. Confidence in locating the epidural space is based on clarity of the loss of resistance and the ease of threading the epidural catheter.

When there is difficulty in advancing the epidural catheter after the epidural space has been identified, several maneuvers are performed in order to correct the problem. These include: injecting saline through the needle to “expand” the epidural space, advancing the needle tip 1-2 mm, inserting a new flexible epidural catheter, inserting a new non-flexible epidural catheter, rotating the needle bevel, changing a patient’s posture, pulling the needle back to re-engage the *ligamentum flavum* and then performing a second LOR technique, and removing the needle entirely and performing a new placement at the same or different interspace (1). Each time a new maneuver is performed, this is considered a new attempt at threading the epidural catheter into the epidural space. Not succeeding on threading the epidural catheter correctly into the epidural space on the very first try is considered a “failure to thread,” however these maneuvers are performed until adequate labor analgesia is established in all patients. Establishing labor analgesia on the first epidural catheter threading attempt reduces the amount of time between when the epidural is requested and when pain relief is administered. A “more successful”

epidural threading attempt is related to a decrease in the time required to thread the epidural and adequately relieve labor pain.

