## **OBJECTIVES**

The aim of the study is to assess if there is a difference in ability to thread the epidural catheter (measured in time to thread) from two different pain management kits: Arrow® and B.Braun®. In order to improve patient care at U of M, if there is a difference in the time to thread epidurals with one kit over the other (i.e. one epidural catheter threads more easily than the other), we would like to use the kit with decreased time to thread in the future. We would like to make this comparison based on data.

Our hypothesis is that there is no difference in the average time required for clinicians to thread the epidural catheters from the Arrow® and B.Braun® pain management kits.

The primary outcome is to compare the number of epidural threading attempts between the Arrow® and B.Braun® pain management kits.

Secondary objectives of this study are to compare the difference in average time required to advance the epidural catheter, the number of epidural needle manipulations once the epidural space has been established, the incidence of unintended dural punctures, the incidence of paresthesia, and the incidence of epidural intravascular cannulations between the two different kit vendors.

Our findings may not be generalizable to other facilities due to local practices (presence or absence of trainees, training level of the residents, obesity of patients, etc.) but data will be made publically available. This project is primarily intended to improve patient care at U of M via scientific level analysis.

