Once, the epidural catheter has been threaded successfully, the clinician will apply negative pressure to the catheter through a syringe in order to rule out blood or cerebro-spinal fluid (CSF) aspiration. If aspiration of blood and CSF is negative, the patient will be given our standard medications consisting of 2 ml Lidocaine 1.5% with epinephrine 1:200,000 to rule out intrathecal catheter placement. Following 2 minutes, the patients will be given additional 3 ml from the lidocaine and epinephrine mixture in order to rule out intravascular cannulation. In addition, a standard loading bolus of bupivacaine 0.125% with fentanyl 3 mcg/ml will be administered in three fractionated doses of 5 ml each, through an epidural pump. All patients will be then connected to a programmed intermittent epidural bolus pump with the following settings: bupivacaine 0.125% with fentanyl 3 mcg/ml, programmed intermittent bolus 6 ml every 45 minutes. Patient's demand bolus 6 ml every 15 minutes, without baseline infusion.

If the epidural catheter cannot be sufficiently advanced into the epidural space, one or more of the following maneuvers will be adopted: additional saline will be administered through the Tuohy needle; alternatively, a new flexible epidural catheter can be inserted; if the catheter advances following one of these afore-mentioned maneuvers, the thread will be considered successful with minor adjustments. Conversely, if the needle is rotated, re-angled, redrawn and

re-advanced or advanced blindly, these will all be considered as major needle manipulations and recorded as failure of that attempt to advance the epidural catheter. Further attempts are made until proper epidural analgesia is established.

Establishment of successful labor analgesia will be defined at a verbal analogue score equal to or less than 10 on a 100-point scale within 30 min from the standard epidural medication administration. All data related to the technical aspects of the epidural placement will be collected in the form shown in the appendix. The goal of both study groups is the management of labor pain.

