## Ease of Threading the Epidural Catheter

- |   |                              |
|---|------------------------------|
|  Easy thread without further maneuvers  |                              |
|  hydrodissection, then catheter:  | Thread Did not thread |
|  new catheter from the same brand, then catheter:   | Thread Did not thread |
|  Rotated the needle, then catheter:   | Thread Did not thread |
|  Changed needle angle, then catheter:   | Thread Did not thread |
|  Withdrawal and re-advanced the needle with an additional LOR (this count as an additional attempt), then catheter: | Thread Did not thread |
|  Advanced the needle blindly, then catheter:  | Thread Did not thread |
|  Changed space  |                              |

Patient Comfort at 30 minutes (VAS  $\leq$  10/100) YES NO

Additional Number of attempts after loss of resistance 0 1 2 3 4 5

Complications (circle all that applies)

Wet tap Paresthesias Intravascular Other (please explain)

Epidural analgesia failed and then epidural Replaced? YES NO

Delivery date \_\_\_ and Time \_\_\_\_\_

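### The number of needle manipulations is a stated objective, but only their incidence is analysed; under the Methods scoring rule that incidence nearly mirrors the primary outcome

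*Combined protocol and SAP*

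**What the plan says.** All sections are in the combined protocol and SAP.

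- **Objectives** lists among the secondary objectives "the number of epidural needle manipulations once the epidural space has been established", which is a count.
- **Statistical Analysis** states that the "primary outcome will be the success rate of epidural catheter threaded with each epidural kit", tested by chi-square or Fisher's exact test. Among the secondary outcomes it tests "the difference in the incidence of epidural needle manipulations once the epidural space has been established" with the same choice of tests. It also compares the number of epidural attempts by Mann-Whitney. It does not define success.
- **Equipment, Technique and Study Data Collection** gives the scoring rule. If the catheter advances after saline or a new flexible catheter, "the thread will be considered successful with minor adjustments". Rotating, re-angling, withdrawing and re-advancing the needle, or advancing it without a further loss of resistance, is scored the other way: "these will all be considered as major needle manipulations and recorded as failure of that attempt to advance the epidural catheter".
- **Background** uses a different idea of failure: "Not succeeding on threading the epidural catheter correctly into the epidural space on the very first try". **Study Size** likewise takes its planning rates from catheters that did not thread on the first attempt.
- **The study form** (Ease of Threading the Epidural Catheter) has one tick line per type of maneuver, for example "Rotated the needle, then catheter", each with a thread / did not thread result. It also has a 0 to 5 field for additional attempts after loss of resistance.

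**The concern.** Two things are at stake.

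First, the objective and the analysis differ. An objective about how many manipulations each kit needs is not met by a test of whether any occurred. The form would not fully support a count even if one were analysed, because two rotations and one rotation leave the same tick. Repeats not noted at the bedside cannot be reliably recovered later.

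Second, the incidence may add nothing to the primary result. If a major manipulation is what makes a placement a threading failure, then manipulation yes/no and success yes/no are two labels for nearly the same event. The report would show a primary and a secondary result that agree because of how they are defined, and a reader could take the second as separate support for the first.

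**Working it through.** **1. The plan's own figure.** Inputs from Study Size: 11% against 1%, alpha 0.05 (two-sided assumed), power 80%. The pooled two-proportion formula gives n = [1.960·√(2·0.06·0.94) + 0.842·√(0.11·0.89 + 0.01·0.99)]² / 0.10² = 87.4. With the continuity correction, n' = (n/4)·[1 + √(1 + 4/(n·0.10))]² = 106.4, rounded up to 107. The stated 107 per group is reproduced, and nothing below changes it.

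**2. Scoring under the Methods rule, per placement.**

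| Course after loss of resistance | Threading | Major manipulation |
|---|---|---|
| Threads at once | Success | No |
| Threads after saline or a new flexible catheter | Success | No |
| Rotated, re-angled, withdrawn and re-advanced, or advanced blindly | Failure | Yes |
| Goes straight to a new interspace | Not stated | Not in the list |

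Apart from the last row and similar gaps, the two columns are complements.

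**3. Size of the overlap.** Take 120 per group and, for illustration only, the Study Size rates: 0.11 × 120 ≈ 13 and 0.01 × 120 ≈ 1. These are rates of not threading on the first attempt; the documents give no rate of major manipulation.

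- Manipulation, 13/120 v 1/120: chi-square p = 0.00095, Fisher p = 0.0014.
- Success, 107/120 v 119/120: chi-square p = 0.00095, Fisher p = 0.0014.

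**4. Scoring under the first-try wording.** A placement rescued by saline or a new catheter is now a failure without a major manipulation. Keep first-try failures at 13 v 1 (Fisher p = 0.0014) and assume a share of the 13 is rescued in that way, leaving the single failure in the other group as a manipulation:

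| Assumed share rescued | Manipulations | Fisher p |
|---|---|---|
| 0% | 13 v 1 | 0.0014 |
| 25% | 10 v 1 | 0.010 |
| 50% | 7 v 1 | 0.066 |
| 75% | 3 v 1 | 0.62 |

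The outcome is then nested in the failures, not their complement.

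**5. What the form can recover.** Four separate lines for major manipulations give 0 to 4 distinct types per placement. Repeats of one type have no field. The 0 to 5 field counts attempts. By the Methods and the form's own note, what adds an attempt after loss of resistance is withdrawal and re-advance to a further loss of resistance, so rotation, re-angling and blind advance are not counted there.

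**6. Would Mann-Whitney on a count suffice?** With 120 per group and 13 v 1 non-zero placements (the 1 having one manipulation), suppose the 13 had one manipulation each, a mix of one to four, or four each. Mann-Whitney p lies between about 0.0009 and 0.0010 throughout, against 0.00095 for the chi-square test of incidence. Now make incidence equal, 13 v 13, with three manipulations each in one group and one each in the other. The means are 39/120 = 0.325 and 13/120 = 0.108, a threefold ratio, yet Mann-Whitney p = 0.77. With mostly zero counts, the rank test sees almost only zero against non-zero. For the same data the difference in means is 0.217, with a 95% percentile bootstrap interval of about 0.05 to 0.40 (placements treated as independent, as in the plan's own tests). The difference in means picks up what the rank test misses.

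**The case against.** The strongest reply is that the duplication is conditional. The analysis section neither defines success nor points to the Methods rule, and the Background and Study Size sections speak of the first try or first attempt. On that reading the two outcomes differ, as step 4 shows. Even under the Methods rule the match is not exact: failure is recorded per attempt, a change of interspace is not listed as a major manipulation, and a change of posture is classed as neither minor nor major. All of this stands, and the point is worded to allow for it.

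A reader might also infer that the number of manipulations is not recorded at all. The documents do not support that. The form distinguishes four types, so it can tell one rotation from a rotation followed by re-angling, re-advance and blind advance, and it counts additional attempts. Only repeats within a type are lost.

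It can further be said that the planned tables and the Mann-Whitney test of attempts already cover the objective. They do so only in part. Table 3 reports success and complications by maneuver, not manipulations per placement. The Background does call every new maneuver an attempt, but the Methods count is narrower.

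Finally, this is a secondary outcome, and no section presents it as independent support. That limits the weight of the point but does not close the gap between objective and analysis.

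**Conclusion.** The mismatch between a number in the objectives and an incidence in the analysis holds under every definition of success, and the form supports the number only as a count of distinct types.

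The overlap with the primary holds in conditional form. If success is scored per placement by the Methods rule, the incidence is essentially the complement of the primary and its test repeats the primary p-value (0.0014 by Fisher in the illustration). If success means first-try threading, the incidence is a nested subset of the failures, and its p-value ranged from 0.0014 to 0.62 over the assumed rescue shares. A reader might infer that the two outcomes must always agree; the first-try wording rules that out. The counts are illustrative, since no rate of major manipulation is given. The primary test and the sample size are untouched. The change is worth making before data collection because it is cheap and missed repeats cannot be restored.

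**What to change.** 1. In Statistical Analysis, state which definition of threading success applies at placement level, and how a placement that goes straight to a new interspace is scored.
2. On the form, replace the ticks for rotated, changed angle, withdrawn and re-advanced, and advanced blindly with counts.
3. Report the number of major manipulations per placement by kit as a distribution (0, 1, 2, and so on) and as a difference in means with a bootstrap or permutation interval. Do not rely on Mann-Whitney alone, for the reason in step 6.
4. If the incidence is kept under the Methods rule, report it descriptively as a component of the primary, without its own p-value. Under the first-try definition, describe it as a subset of the failures.

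Cost: a few sentences in the analysis section, four changed lines on the form, and slightly more recording by the operator. No additional placements are needed.
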